16.1.2 Descriptive Statistics of PK Parameter Data

PK parameter data will be descriptively summarized using: number of non-missing observations (n), arithmetic mean (Mean), standard deviation (SD), coefficient of variation (CV%), minimum (Min), median (Median), maximum (Max), geometric mean (GeoMean), the geometric coefficient of variation (GeoCV) and the 95% confidence interval for the GeoMean (95% CI GeoMean). For PK parameters related to time (e.g. t_{max} , t_{last}), only n, Min, Median, and Max may be reported.

Descriptive statistics will only be calculated for a PK parameter when $n > 2$. In case $n \leq 2$, individual data will be presented (min, max) in summary tables.

PK parameters read directly from the measurements (i.e. C_{max}) will be reported with the same precision as the source data. All other PK parameters will be reported to 3 significant figures.

Descriptive statistics of PK parameter data will be calculated using full precision and rounded for reporting purposes only.

PK parameters will be provided with full precision, without any rounding applied to CDISC SDTM PP and ADaM PP domains.

The following conventions will be applied when reporting descriptive statistics of PK parameter data:

n:	0 decimal place
Mean, Min, Median, Max, SD, GeoMean, 95% CI:	3 significant digits
CV%, GeoCV%:	1 decimal place

16.1.3 General Specifications for PK Concentration and PK Parameter Data

Predose samples that occur before the drug administration will be assigned a time of 0 hours, as if the sample had been taken simultaneously with the study drug administration.

Values below the lower limit of quantification (BLQ) will be taken as zero for summary statistics of PK concentration data, PK parameter estimation (e.g. AUC) and for graphical presentations. It is expected that samples with concentrations above the ULOQ will be diluted and retested.

Missing concentrations (e.g. no sample, insufficient sample volume for analysis, no result or result not valid) will be reported and used generally as "N.R.". A participant who withdraws prior to the last planned observation will be included in the analyses up to the time of discontinuation.

Samples that are collected outside the specified time windows specified in the CSP will be included in the PK parameter estimation (NCA) but will be excluded from the concentration summary and mean concentration plots.

PK concentrations which are erroneous due to a protocol violation (as defined in the CSP), sampling processing or analytical error (as documented in the bioanalytical report) may be excluded from the PK analysis if agreed by the Sponsor. In this case the rationale for exclusion must be provided in the CSR. Any other PK concentrations that appear implausible to the Clinical Pharmacologist/Clinical PK/PD Scientist will not be excluded from the analysis. Any implausible data will be documented in the CSR.

If samples are collected outside of 10% of its nominal time point, these will be included in the PK parameter estimation (NCA) but will be excluded from the concentration summary and mean/median concentration plots.

Any PK concentrations or PK parameters excluded from summary statistics will be included in subject listings and flagged; a reason for exclusion will be detailed in the CSR (e.g. a footnote or

a table of exclusions). Any flags should be included in the study specific SDTM and ADaM data sets.

PK concentrations and PK parameters excluded from summary statistics will not be included in combined individual and mean figures. Mean plots will only contain averages when $n > 2$.

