## 7.2 Participant Discontinuation/Withdrawal from the Study

- The participant may withdraw from the study at any time, at his/her own request or may be withdrawn at any time at the discretion of the Investigator for safety, behavioral, compliance, or administrative reasons.
- The participant may be withdrawn by the Investigator due to participation in another clinical study.
- If a participant has failed to attend scheduled study assessments, the Investigator must determine the reasons and the circumstances as completely and accurately as possible.
- If a participant must be withdrawn from the study, the Sponsor Medical Responsible and Clinical Study Lead will be informed immediately.
- If there is a medical reason for the withdrawal, appropriate medical care will be provided.
- At the time of discontinuing from the study, if possible, a discontinuation visit will be conducted, as listed in the SoA. The SoA specifies the data to collect at study discontinuation and follow-up, and any additional evaluations that need to be completed.
- If the participant withdraws consent for future involvement in the study, any data collected up to that point may still be used, but no future data can be generated, and any biological samples collected will be destroyed.
- A participant has the right at any time to request destruction of any biological samples taken. The Investigator will document this in the site study records.

The Investigator will secure the safety of the study participants and make every attempt to collect the data.

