9.5 Imputation of Missing Data

In this Phase I PK study, missing observations will be assumed to be missing completely at random (MCAR). No action will be taken to handle missing data. A participant who withdraws prior to the

last planned observation in a study period will be included in the analyses up to the time of discontinuation.

Missing statistics, e.g. when they cannot be calculated, should be presented as “ne”. For example, if $n=1$, the measure of variability (SD) cannot be computed and should be presented as “ne”.

Incomplete AE-related dates will be imputed as follows:

- In case the onset date is missing completely or missing partially but the onset month and year, or the onset year are equal to the start of study intervention then the onset date will be imputed by the minimum of start of study intervention and AE resolution date (if not missing).
- In all other cases, the missing onset day or missing onset month will be imputed by 1.
- Incomplete stop dates will be imputed by the last day of the month (if day is missing only), if not resulting in a date later than the date of participant’s death. In the latter case, the date of death will be used to impute the incomplete stop date.
- In all other cases, the incomplete stop date will not be imputed.

There will be no imputation for missing or incomplete dates for prior or concomitant therapies.

For the derivation of previous and concomitant therapies the following rules will be applied:

Previous therapy:

- Start date \leq Start of study med OR
- Start date = Missing

Concomitant therapy:

- End date \geq Start of study med. AND (Start date \leq End of study med OR Start date=Missing) OR
- End date = Missing AND (Start date \leq End of study med. OR Start date = Missing)

The derivation is based on the following principles

- Imputation leads to max. reasonable duration
- Worst case: If medication is administered the same day as start of study medication, medication is classified as concomitant and prior

There will be no imputation for missing or incomplete dates for date of study intervention.

10 Study Participants

The subsections in this section include specifications for reporting participant disposition and study intervention/study discontinuations. Additionally, procedures for reporting protocol deviations are provided.

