16.1.4.1 Estimation of Pharmacokinetic Parameters in Plasma

PK parameters will be calculated using the actual elapsed time since dosing, given with a precision of 4 decimal places or the SAS format Best12. In cases where the actual sampling time is missing, calculations will be performed using the scheduled time. Otherwise, there will be no further imputation of missing data.

The following PK parameters will be calculated where appropriate from xevinapant and its metabolite D-1143-MET1 plasma concentrations:

Symbol	Definition
$AUC_{0-t_{last}}$	The area under the concentration-time curve (AUC) from time zero (= dosing time) to the last sampling time (t_{last}) at which the concentration is at or above the lower limit of quantification. Calculated using the mixed log-linear trapezoidal rule (linear up, log down).
$AUC_{0-\infty}$	The AUC from time zero (dosing time) extrapolated to infinity, based on the predicted value for the concentration at t_{last} , as estimated using the linear regression from λ_z determination. $AUC_{0-\infty} = AUC_{0-t} + C_{last\ pred} / \lambda_z$.
AUC_{0-24}	The area under the concentration-time curve (AUC) from time zero (= dosing time) to 24 hours. Calculated using the mixed log-linear trapezoidal rule (linear up, log down).
$AUC_{extra\%}$	The AUC from time t_{last} extrapolated to infinity given as percentage of $AUC_{0-\infty}$. $AUC_{extra\%} = (\text{extrapolated area} / AUC_{0-\infty}) * 100$.

Symbol	Definition
CL/F	The apparent total body clearance of study intervention following extravascular administration, taking into account the fraction of dose absorbed. $CL/F = \text{Dose}_{p.o.} / AUC_{0-\infty}$ (xevinapant only).
C_{max}	Maximum observed concentration.
t_{max}	The time to reach the maximum observed concentration collected during a dosing interval (unless otherwise defined, take the 1 st occurrence in case of multiple/identical C_{max} values).
t_{last}	The last sampling time at which the concentration is at or above the lower limit of quantification.
C_{last}	The observed concentration at the last sampling time (t_{last}) at which the concentration is at or above the lower limit of quantification.
$t_{1/2}$	Apparent terminal half-life. $t_{1/2} = \ln(2) / \lambda_z$.
λ_z	Terminal first order (elimination) rate constant. Determined from the terminal slope of the log-transformed concentration curve using linear regression on terminal data points of the curve.

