V_z/F	The apparent volume of distribution during the terminal phase following extravascular administration, based on the fraction of dose absorbed. $V_z/F = \text{Dose} / (AUC_{0-\infty} * \lambda_z)$ following single dose (xevinapant only).
MR($AUC_{0-t_{last}}$)	Metabolic ratio of $AUC_{0-t_{last}}$. $AUC_{0-t_{last}}$ for D-1143-MET1 divided by the $AUC_{0-t_{last}}$ of xevinapant corrected for MW. $MR(AUC_{0-t_{last}}) = AUC_{xevinapant} * MW_{xevinapant} / AUC_{D-1143-MET1} * MW_{D-1143-MET1}$ where $MW_{xevinapant} = 561.71 \text{ g/mol}$ $MW_{D-1143-MET1} = 476.61 \text{ g/mol}$
MR($AUC_{0-\infty}$)	Metabolic ratio of $AUC_{0-\infty}$. $AUC_{0-\infty}$ for D-1143-MET1 divided by the $AUC_{0-\infty}$ of xevinapant corrected for MW. $MR(AUC_{0-\infty}) = AUC_{xevinapant} * MW_{xevinapant} / AUC_{D-1143-MET1} * MW_{D-1143-MET1}$ where $MW_{xevinapant} = 561.71 \text{ g/mol}$ $MW_{D-1143-MET1} = 476.61 \text{ g/mol}$
MR(C_{max})	Metabolic ratio of C_{max} . C_{max} for D-1143-MET1 divided by the C_{max} of xevinapant corrected for MW. $MR(C_{max}) = C_{max,xevinapant} * MW_{xevinapant} / C_{max,D-1143-MET1} * MW_{D-1143-MET1}$ where $MW_{xevinapant} = 561.71 \text{ g/mol}$ $MW_{D-1143-MET1} = 476.61 \text{ g/mol}$

Partial areas should be calculated using the nominal dosing interval. The actual dosing interval calculated from case report form (CRF) time data should not be used.

The following PK parameters will be calculated for diagnostic purposes and listed, but will not be summarized:

- First ($\lambda_{z \text{ low}}$) and last ($\lambda_{z \text{ up}}$) time point of the time interval of the log-linear regression to determine λ_z .
- Number of data points (N_i) included in the log-linear regression analysis to determine λ_z .
- Goodness of fit statistic (adjusted Rsq) for calculation of λ_z .
- Span ratio.

The regression analysis should contain data from at least 3 different time points in the terminal phase consistent with the assessment of a straight line on the log-transformed scale. Phoenix WinNonlin “best fit” methodology will be used as standard. However, in some cases, further adjustment may be made by the pharmacokineticist, if warranted, after agreement with the Sponsor. The last quantifiable concentration should always be included in the regression analysis, while the concentration at t_{max} and any concentrations <LLOQ which occur after the last quantifiable data point should not be used.

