If $\text{AUC}_{\text{extra}\%} > 20\%$ and/or the coefficient of correlation (Rsq adj) of λ_z is < 0.8 and/or the observation period over which the regression line is estimated is less than two-fold the resulting $t_{1/2}$, the rate constants and all derived parameters (e.g. $t_{1/2}$, $\text{AUC}_{0-\infty}$, CL/F etc.) will be listed, flagged and included in the parameter outputs and may be excluded from descriptive statistics.

In case profiles have a measurable pre-dose concentration less than or equal to 5% of its C_{max} value, the participant’s data without any adjustments will be included in all PK measurements and calculations. If the pre-dose value is greater than 5% of the C_{max} , the participant will be dropped from all PK evaluations. However, this participant’s data will be flagged and reported.

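### Could a participant withdrawn within hours of dosing distort the AUC0-tlast summary, given that the SAP sets no rule for partial areas?

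*SAP*

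**What the plan says.** SAP 16.1.3 sets the default for someone who leaves early: "A participant who withdraws prior to the last planned observation will be included in the analyses up to the time of discontinuation". SAP 9.5 says the same of anyone who leaves before the "last planned observation in a study period will be included in the analyses up to the time of discontinuation". It assumes missing values are missing completely at random and plans no handling of them. Entry to the PK Analysis Set (SAP 8.1) needs one dose and one measurable postdose concentration.

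SAP 16.1.4.1 ends AUC0-tlast at the last sampling time "at which the concentration is at or above the lower limit of quantification", with no minimum coverage. The same section sets three quality limits: extrapolated area above 20%, adjusted R-squared below 0.8, and a regression window shorter than two half-lives. These apply to the terminal rate constant and whatever is derived from it, including AUC0-∞. Parameters that fail "will be listed, flagged and included in the parameter outputs and may be excluded from descriptive statistics". AUC0-tlast does not depend on the terminal slope, so the limits do not reach it.

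Several other passages bear on the point:

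- Protocol 4.1 keeps participants in the unit until about 72 h after dosing.
- Protocol 7.2 states that on withdrawal of consent "no future data can be generated, and any biological samples collected will be destroyed".
- Protocol 9.3 leaves exclusions from analysis sets to a data review meeting before lock.
- SAP 10.2.1 counts failure to collect data needed for the primary endpoints as an important deviation, and lets the meeting flag PK values for exclusion.
- SAP 16.1.3 requires excluded values to be listed and flagged, with the reason in the study report.

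**The concern.** Read literally, a participant whose sampling stops at 4, 8 or 12 h with drug still measurable contributes a partial area to the summary of a primary endpoint. The error can only go downward. With about 12 per group, one such value lowers the geometric mean of one ethnic group for a reason unrelated to ethnicity, and the purpose of the study is to describe exposure by ethnic group.

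The plan also looks uneven. For the same profile, one primary AUC (AUC0-∞) would be flagged and could be left out, while the other (AUC0-tlast) would be summarised without a flag. Discretion to remove it exists, but no criterion is written down.

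**Working it through.** **1. The plan's own figure.** Protocol 9.2 assumes a CV of 35%, so the log-scale SD is σ = √ln(1 + 0.35²) = 0.340. With 10 per group, the 90% CI half-width at 80% probability is t(0.95, 18) × σ × √(2/10) × √(χ²(0.80, 18)/18) = 1.734 × 0.340 × 0.447 × 1.124 = 0.296. Then exp(±0.296) gives 0.7435 to 1.3451, as in Table 1. The same σ is used below.

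**2. Which events shorten the area.** The sampling times after 12 h are 24, 36, 48 and 72 h (Protocol 1.3). AUC0-tlast stops at 12 h or earlier only if all of these are absent. Missed Day 1 samples in someone who stays do not truncate it: removing the 4, 6, 8 and 12 h samples from the model below still leaves 99 to 100% of the area. Withdrawal of consent leads to destruction of the samples. What remains is withdrawal for another reason, such as by the investigator, within about 12 h of dosing.

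**3. Share of the area captured.** Inputs are half-life 6 to 8 h and tmax 1 to 2 h (Protocol 2.2, reported in patients with cancer). The one-compartment oral model is an assumption: C(t) ∝ exp(−kt) − exp(−kₐt), with k = ln 2/half-life and kₐ solved from tmax = ln(kₐ/k)/(kₐ − k). Areas use the linear-up, log-down rule on the protocol's sampling times, and f = AUC to the last sample ÷ AUC0-72.

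**4. Effect on a group of 12.** One truncated profile multiplies the geometric mean by f^(1/12). The standard error of the log-mean is 0.340/√12 = 0.098. For half-life 8 h, tmax 2 h and a stop at 12 h, f = 0.626. The log shift is ln(0.626)/12 = −0.039, or −3.8%, and 0.039/0.098 = 0.40 standard errors.

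| Last sample | Share of AUC0-72 | Shift, 1 of 12 | In standard errors | Extrapolated area |
|---|---|---|---|---|
| 4 h | 25–35% | −8 to −11% | 0.90–1.18 | 65–79% |
| 8 h | 47–59% | −4 to −6% | 0.45–0.64 | 41–53% |
| 12 h | 63–74% | −2.5 to −4% | 0.26–0.40 | 26–38% |
| 24 h | 87–94% | about −1% | 0.06–0.12 | 6–13% |

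In the overall summary, one of 24 stopping at 12 h shifts the mean by −1 to −2%. For scale, the 95% CI of a geometric mean at n = 12 runs from 0.81 to 1.24 times the estimate.

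**5. Would anyone notice?** At 12 h or earlier the extrapolated area exceeds the SAP's 20% limit. At 12 h the regression window spans only 1.0 to 1.75 half-lives, below the limit of two. The companion AUC0-∞ is therefore flagged. SAP 16.1.2 names tlast among the time parameters summarised by n, minimum, median and maximum, so a stop at 12 h would appear as a low minimum. SAP 16.1.6.1 lists individual parameters and sampling times, and the median AUC is reported beside the geometric mean. At 24 h no flag is raised, and the shift is about 1%.

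**6. Would a fixed exclusion gain precision?** At 12 h, no. Keeping the truncated profile gives an expected 95% CI factor between 0.79–1.26 and 0.80–1.25. Dropping it (n = 11) gives 0.80–1.26.

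**The case for a change.** The best case for a preset rule is about discipline more than size. The study is open label, so the data review would decide on a partial area knowing the ethnic group. The SAP sets firm rules elsewhere: a predose value above 5% of Cmax removes the participant from the PK evaluation. Comparison with historical non-Asian data may follow, and there a downward artefact could be read as an ethnic difference. A stop at 4 h would cost 8 to 11%, and two of 12 stopping at 12 h would cost 5 to 7.5%. A rule would take a few sentences.

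It stands that the default is written down, that AUC0-tlast lies outside the quality limits, and that no numeric criterion exists. The larger shifts carry little weight. They need withdrawal within hours of one dose, during confinement, for a reason other than withdrawn consent. None of the events reported in 58 healthy participants was serious or severe (Protocol 2.3). The 17% drop-out allowance covers the whole study, so it does not support a scenario in which both expected leavers go on the dosing day.

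Mandatory exclusion is not free of assumptions either. It is unbiased only if leaving is unrelated to exposure. A case-by-case decision, with the value listed and the reason reported, is a fair alternative. The plan's "The following PK parameters will be calculated where appropriate from xevinapant and its metabolite D-1143-MET1 plasma concentrations" also leaves the pharmacokineticist room not to report an area that does not represent the profile.

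**Conclusion.** No change follows. The SAP leaves out a detail that the data review can fill sensibly before lock, through deviation and flagging routes it already contains. The profile at issue would be hard to miss. If it occurred and stayed in, a stop at 12 h in one of 12 participants would lower the group geometric mean of AUC0-tlast by 2.5 to 4%, well inside the interval of 0.81 to 1.24. A stop at 4 h would cost 8 to 11%, but it would be the most conspicuous case at review. The primary analysis is descriptive, with no hypothesis (Protocol 9.1) and no formal PK testing (SAP 16.1.5), so its conclusions remain sound.

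This rests on one-compartment kinetics and on half-life and tmax values from patients with cancer. The LLOQ is not given. The modelled 12 h concentration is 29 to 45% of Cmax, so it is very likely still quantifiable. The documents give no rate of early withdrawal, and its rarity is inferred from confinement and the earlier tolerability data. No figure is offered for D-1143-MET1, or for the metabolic ratio of AUC0-tlast, because the metabolite's half-life is not stated.

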### 1.3

### Schedule of Activities

Assessments & Procedures	Screening	Admission to CRU					SFU (Televisit)	Notes
Study Day	-28 to -3	-1	1	2	3	4 (EoT)	8 (-1 / +2 days)	
Written informed consent	X							Informed consent to be available before start of any study specific assessments.
Participants resident at CRU		X	X	X	X	X		Admission to CRU in the afternoon on Day -1 until discharge on Day 4 after completion of all study-related activities
Inclusion and exclusion criteria	X	X						Recheck clinical status before administration
Demography	X							Including age (year of birth), sex, race and ethnicity
Full physical examination	X	X				X		
Medical history	X							
Pregnancy test	X	X				X		Pregnancy test using serum (at Screening) and using urine (on Day -1 and End of Study), to confirm non-pregnant status (females only)
Follicle stimulating hormone	X							To confirm postmenopausal status (females only)
Serology	X							HIV, hepatitis B and C SARS-CoV-2
Drug and alcohol screen	X	X						
Clinical laboratory tests a	X	X	X	X		X		After at least 10 hours fasting, Day 1 sampling is predose
Safety 12-Lead ECG	X		X	X		X		Day 1: predose, 1 hour postdose, Day 2 (24 hours postdose), and Day 4 (72 hours postdose) (see Section 8.2.3 for further details)

Assessments & Procedures	Screening	Admission to CRU					SFU (Televisit)	Notes
		-1	1	2	3	4 (EoT)		
Study Day	-28 to -3	-1	1	2	3	4 (EoT)	8 (-1 / +2 days)	
Vital signs	X	X	X	X	X	X		Height and Weight to be collected at Screening only. Day 1: predose, 1, 2, 4, 12 hours; Day 2: 24 hours, Day 3: 48 hours, Day 4: 72 hours
CCI								
Study intervention			X					
AE & SAE review	X	X	X	X	X	X	X	
Concomitant medications review	X	X	X	X	X	X	X	
PK blood sampling (plasma)			X	X	X	X		Day 1: predose, and 0.25, 0.5, 1.0, 1.5, 2, 2.5, 3, 4, 6, 8, and 12 hours postdose; Day 2: 24 and 36 hours postdose; Day 3: 48 hours postdose, Day 4: 72 hours postdose. See Section 8.4 for collection windows and further details. The time and date of each collection to be recorded in eCRF.

aUrine samples will be collected at Screening and times of other clinical labs.

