Xevinapant is an antagonist of IAPs with chemosensitizing, radiosensitizing, and immunomodulatory activities. Nonclinical studies in several in vitro and in vivo SCCHN models demonstrated an efficient antiproliferative activity and a synergistic enhancement of intrinsic cellular radiation sensitivity when xevinapant was combined with RT. The synergistic effect of xevinapant combined with RT in vivo was able to cure tumors in 8 of 10 xenografted mice without any apparent toxicity whereas all mice died with RT alone ([Matzinger 2015](#)). These results indicate that xevinapant in combination with RT has a promising therapeutic potential in the treatment of SCCHN.

Based on current understanding of the mechanism of action, the value of adding xevinapant to platinum-based conventional CRT in the treatment of previously untreated patients with non-resected LA SCCHN has been investigated in a Phase 1-2 study (Debio 1143-201, refer to IB for further details). The Phase 2 part of Debio 1143-201 study (part B of the study) was a randomized, placebo-controlled, double-blind study. Efficacy results from the 24-month primary analysis have shown antitumor activity of xevinapant: patients treated with xevinapant were around 2.5 times more likely to have locoregional control 18 months after completing treatment, compared with patients having received a placebo. The ongoing global Phase 3 study TrilynX aims to confirm the value of xevinapant in the treatment of previously untreated LA SCCHN patients (including those from East Asia) with hypopharynx, larynx and/or HPV-16 negative OPC, who are suitable for definitive CRT and are more likely to relapse locally.

Xevinapant PK has been evaluated in clinical studies in patients with cancer, either as monotherapy or in combination with other cancer treatments, after once daily oral administration on Days 1 to 5, on Days 1 to 14 of 3-week cycles and on Days 1 to 10 and Day 15 to 24 of 4-week cycles (refer to IB). Xevinapant was well absorbed with  $t_{max}$  reached in about 1 to 2 hours. In the monotherapy treatment, PK of xevinapant was dose-proportional in the dose

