range 100 to 900 mg. Half-life ( $t_{1/2}$ ) is about 6 to 8 hours. In monotherapy, no accumulation after multiple dosing was observed. Apparent clearance was low, indicating a limited hepatic extraction. Renal clearance was low, with about 8% to 10% of xevinapant recovered unchanged in urine. In vitro binding of xevinapant to human plasma proteins was moderate (84% to 88%). D-1143-MET1, a metabolite with no significant antagonistic IAP activity in vitro, is a major circulating metabolite in human, with plasma exposure of the same order of magnitude as xevinapant. D-1143-MET1 formation from xevinapant is essentially extrahepatic. Xevinapant is a low permeability drug. In general, interindividual variability in PK disposition was large for xevinapant and its major metabolite D-1143-MET1 in cancer patients (e.g., 50 to 80 geoCV% for xevinapant  $AUC_{0-t}$ ), but lower (35 geoCV% for  $AUC_{0-t}$ ) in Caucasian healthy participants.

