The exact date/time of sample collection and study intervention (24-hour clock time) must be recorded in the eCRF and will be used in the calculation of PK parameters. The accepted time deviations from planned PK times that will not be considered a protocol violation are listed below:

Procedure	Time Point (Relative Time)	Window Allowance
Pharmacokinetics	Predose	- 90 min
	0.5 to 2 hours postdose	- / + 2 min
	> 2 to 12 hours postdose	- / + 5 min
	> 12 to 72 hours postdose	- / + 15 min

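### Do the two sampling-time limits in SAP 16.1.3, and the missing 0.25 h row in the protocol's window table, call for a change?

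*SAP*

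**What the plan says.** Two paragraphs of SAP 16.1.3 deal with mistimed samples. The first concerns "Samples that are collected outside the specified time windows specified in the CSP"; these stay in the non-compartmental analysis (NCA) but leave the concentration summary and the mean plots. The second reads "If samples are collected outside of 10% of its nominal time point, these will be included in the PK parameter estimation (NCA") and again removes the sample from the summary, this time naming mean/median plots. Neither paragraph refers to the other.

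The windows are in Protocol 8.4.2, introduced by "The accepted time deviations from planned PK times that will not be considered a protocol violation are listed below". Apart from predose, the rows are "0.5 to 2 hours postdose" (2 min either way), over 2 to 12 h (5 min) and over 12 to 72 h (15 min). The Schedule of Activities (Protocol 1.3) lists "Day 1: predose, and 0.25, 0.5, 1.0, 1.5, 2, 2.5, 3, 4, 6, 8, and 12 hours postdose", then 24, 36, 48 and 72 h, and points to Section 8.4 for windows. None is given for 0.25 h there or elsewhere.

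For the parameters, SAP 16.1.4.1 states that "PK parameters will be calculated using the actual elapsed time since dosing".

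**The concern.** Two limits of very different width, with no stated order between them, invite the question of which one the programmer applies. If the 10% rule were taken to replace the windows, a 24 h sample could be 144 min off and a 72 h sample 432 min off and still enter a mean plotted at nominal time. With the protocol's half-life, which "is about 6 to 8 hours", such late samples would read 19–24% and 46–57% low.

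The missing 0.25 h row adds to the doubt. That sample falls in the absorption phase, since tmax is "reached in about 1 to 2 hours", and a minute matters more there than late in the profile. The table also serves as the list of accepted deviations, so the protocol does not say what timing error is tolerated at 0.25 h. Extending the 2 min row to that time would let a sample 1.5 to 2 min off comply with the protocol and still fail the 10% rule.

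**Working it through.** **Step 1: compare the limits at every scheduled postdose time.** The 10% limit in minutes is 0.10 × t × 60, with t in hours. Windows are from Protocol 8.4.2.

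| Time (h) | Protocol window (min) | 10% limit (min) | Tighter |
|---|---|---|---|
| 0.25 | none | 1.5 | 10% (only limit) |
| 0.5 | 2 | 3 | window |
| 1, 1.5, 2 | 2 | 6, 9, 12 | window |
| 2.5, 3, 4 | 5 | 15, 18, 24 | window |
| 6, 8, 12 | 5 | 36, 48, 72 | window |
| 24, 36 | 15 | 144, 216 | window |
| 48, 72 | 15 | 288, 432 | window |

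The window is tighter at all 14 times that have one, and 0.25 h is covered by the 10% rule. Predose samples are assigned time 0 (SAP 16.1.3), so the 10% rule raises nothing there.

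**Step 2: what the limits in force allow late in the profile.** A sample late by d hours in the terminal phase is low by 1 − 2^(−d/t½). With t½ of 6 and 8 h:

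- d = 0.25 h (the 15 min window): 2.8% and 2.1%.
- d = 2.4 h (10% of 24 h): 24.2% and 18.8%.
- d = 7.2 h (10% of 72 h): 56.5% and 46.4%.

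Only the first line describes the plan. The other two would need the window rule to be set aside.

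**Step 3: size at 0.25 h.** Assume one compartment with first-order absorption, C(t) ∝ exp(−ke·t) − exp(−ka·t), where ke = ln 2/t½ and ka solves ln(ka/ke)/(ka − ke) = tmax. Take tmax 1 to 2 h and t½ 6 to 8 h. For a single sample, 1.5 min off changes the concentration by 5.5–8.4%, and 2 min off (13.3% of nominal) by 7.2–11.3%.

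Assume timing errors are normal with mean 0 and SD 1 min (range 0.5 to 2). Then P(|error| > 1.5 min) is 13.4% (0.3–45%) and P(|error| > 2 min) is 4.6% (0.006–32%). At SD 1 min that is 1.3 and 0.5 of 10 samples.

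The summary reports a mean, so the errors must be averaged. Integrating C(0.25 h + error)/C(0.25 h) over the normal error distribution (SD 1 min) gives 0.9987–0.9993 of the on-time mean with no exclusion, and 0.9993–0.9996 when samples beyond 1.5 min are dropped. In each scenario the difference is below 0.1%, because early and late samples nearly cancel.

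For precision, assume the 35% CV that Protocol 9.2 uses for PK parameters. The relative standard error is 35/√10 = 11.1% with ten samples and 35/√9 = 11.7% with nine.

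**Step 4: follow an excluded sample.** It stays in the NCA at actual elapsed time (SAP 16.1.3, 16.1.4.1). It appears flagged in the listings, with the reason reported in the CSR (16.1.3). Actual time, nominal time and deviation are listed for each sample (16.1.6.1). No objective or endpoint is a concentration at a fixed time (SAP 5), and no formal analysis of PK parameters is planned (16.1.5).

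**The case for a change.** The best case for a change is that one sentence before database lock would remove all doubt. On the literal reading the 10% rule does nothing at 14 of 15 times, and a reader may suspect that a rule with so little work was meant as the operative one. SAP 16.1.3 also lets the sponsor exclude concentrations made erroneous by a protocol violation, so the unclassified 0.25 h deviation might seem able to reach the NCA.

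The omission itself stands: the table has no 0.25 h row and the schedule has a 0.25 h sample. The rest carries little weight. Applying only the 10% rule means disregarding an explicit paragraph of the same section. The clause on erroneous concentrations does not displace the specific instruction to keep mistimed samples, and a value with a recorded actual time is mistimed, not erroneous. The conflict between a compliant sample and the 10% rule arises only if someone writes a 2 min window that no document contains. Even then, a display rule may be stricter than a deviation rule. Relying on the windows alone would be worse, because it would remove the only limit at 0.25 h.

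The upper end of the timing range (SD 2 min, 45% of 0.25 h samples dropped) would cost the 0.25 h mean real precision. But it also implies missing the 2 min windows from 0.5 to 2 h about a third of the time (32%), a conduct problem that no wording in 16.1.3 would cure.

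**Conclusion.** No change to the plan is needed. The two exclusions are compatible. Applied as written, they give one definite limit at each of the 15 postdose times: the protocol window at 14 and 1.5 min at 0.25 h. A sentence calling them cumulative would restate what the section already produces. The difference between mean and mean/median plots is immaterial, since SAP 16.1.6.2 plans only mean plots.

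The missing 0.25 h row is a clerical slip in the protocol. It leaves the accepted timing deviation at that time unstated and affects no PK parameter or endpoint. What the rules can move is the n and mean at 0.25 h: about 1.3 of 10 samples and under 0.1% of the mean at a timing SD of 1 min.

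Those two figures rest on the one-compartment model, the assumed timing SD, and tmax and half-life values that the protocol reports from patients. The conclusion that the endpoints are untouched rests on none of these. It follows from keeping every mistimed sample in the NCA at its actual time.
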